1. ABBREVIATIONS

Abbreviation	Term
ADaM	Analysis Data Model (a CDISC standard)
AE	adverse event
BBMD	bladder and bowel movement diary
BM	bowel movement
BMI	body mass index
BSFS	Bristol Stool Form Scale
CDISC	Clinical Data Interchange Standards Consortium
cGMP	cyclic guanosine monophosphate
CI	confidence interval
CRO	clinical research organization
CRP	C-reactive protein
CRU	clinical research unit
CTCAE	Common Terminology Criteria for Adverse Events
DMC	data monitoring committee
ECG	electrocardiogram
eCRF	electronic case report form
ESR	erythrocyte sedimentation rate
GC-C	guanylate cyclase C
IC/BPS	interstitial cystitis/bladder pain syndrome
ICF	informed consent form
IPD	important protocol deviations
ITT	intention-to-treat
LLN	lower limit of normal
MedDRA	Medical Dictionary for Regulatory Activities
MRP	multidrug resistance protein
PCS	potentially clinically significant
PD	pharmacodynamic
PK	pharmacokinetic
PT	preferred term
QTcF	QT Interval corrected for heart rate using Fridericia's formula
SAE	serious adverse event

Abbreviation	Term
SAP	statistical analysis plan
SD	standard deviation
SE	standard error
SI	Système International
SOC	system organ class
SDTM	Study Data Tabulation Model (a CDISC standard)
TEAE	treatment-emergent adverse event
TESAE	treatment-emergent serious adverse event
ULN	upper limit of normal

2. INTRODUCTION

Study C3300-101 is a Phase 1, placebo-controlled study of the safety and tolerability of rectally-administered single-ascending doses of IW-3300 in healthy volunteers.

IW-3300 is being developed for the treatment of bladder pain associated with interstitial cystitis/bladder pain syndrome (IC/BPS). IW-3300 is a novel, 13-amino-acid, guanylate cyclase C (GC-C) agonist peptide. GC-C, the target of IW 3300, is predominantly expressed on the luminal surface of the small and large intestines. When GC-C receptors are stimulated, intracellular cyclic guanosine monophosphate (cGMP) is secreted across the basolateral membrane of colonic epithelial cells in the submucosa by multidrug resistance proteins (MRP)4 and MRP5, decreasing the activity of afferent nerve fibers located in the colonic wall, resulting in reduced visceral pain, which ultimately produces an analgesic effect in other organs of the abdominopelvic region via action mediated through the common afferent pathways.

This statistical analysis plan (SAP) was developed in accordance with ICH E9 guideline. All decisions regarding final analysis, as defined in this SAP document, will be made prior to database lock and unblinding of the study data. Further information can be found in the protocol.

This SAP describes the statistical analysis methods for the analysis of safety and pharmacodynamic (PD) data. The statistical analysis methods for the pharmacokinetics (PK) assessments will be described in a [PK analysis plan](#). The data are collected as described in the following documents:

- [Study protocol version 4/amendment 3](#) dated 10 January 2022
- electronic case report form (eCRF) version 1.02 dated 19 Jan 2022.

The final SAP must be finalized, approved by the sponsor, Ironwood Pharmaceuticals, Inc. and formally archived before database is locked. Deviations from the final approved plan will be noted in the clinical study report.

3. OBJECTIVES, ESTIMAND(S), AND ENDPOINTS

3.1. Objectives

3.1.1. Primary Objective

To assess the safety and tolerability of single ascending doses of IW-3300 administered rectally via enema in healthy volunteers.

3.1.2. Exploratory Objectives

- To summarize the single-dose pharmacokinetics of IW-3300 administered rectally via enema in healthy volunteers.
- To summarize the single-dose pharmacodynamics of IW-3300 administered rectally via enema in healthy volunteers based on bladder and bowel assessments.

3.2. Endpoints

3.2.1. Safety Endpoints

- Incidence of treatment-emergent adverse events (TEAEs)
- Incidence of treatment-emergent serious adverse events (TESAEs)

3.2.2. Pharmacokinetic Endpoints

- Area under the plasma concentration time curve from time zero to the time at which the last measurable concentration is observed (AUC_{0-t})
- Area under the plasma concentration time curve from time zero to time infinity ($AUC_{0-\infty}$)
- Maximum plasma concentration (C_{max})
- Time to maximum plasma concentration (T_{max})
- Terminal elimination half-life ($t_{1/2}$)
- Total amount of IW-3300 in stool (concentration and percent recovery)

3.2.3. Pharmacodynamics Endpoints

- Change from baseline in bowel movement (BM) frequency during the Clinic Period
- Change from baseline in stool consistency (Bristol Stool Form Scale [BSFS] score) during the Clinic Period
- Change from baseline in urinary frequency during the Clinic Period for a 24-hour duration
- Change from baseline in urinary urgency during the Clinic Period for a 24-hour duration
- Change from baseline in nocturia during the Clinic Period for a 24-hour duration

- Change from baseline in pain or burning in bladder or pelvic area during the Clinic Period for a 24-hour duration

4. STUDY DESIGN

4.1. GENERAL DESCRIPTION

This is a Phase 1, single-center, randomized, double-blind, placebo-controlled, single-ascending dose study assessing the safety, tolerability, and PK of IW-3300 administered rectally as a low volume enema in healthy adult volunteers. Each cohort will progress through 3 study periods: (1) Screening Period, (2) Clinic Period, and (3) Follow-up Period; these periods and the progression between cohorts are illustrated in the study schematic ([Figure 1](#)).

This first-in-human study in healthy adult volunteers will assess all subjects for safety, PK, and effect on stool frequency/form and urination.

A Dose Escalation Committee will conduct blinded reviews of all the safety/tolerability parameters of the dosing cohort through Discharge (Day 2) in order to make decisions regarding dose escalation. Following blinded review, safety data for individual subjects may be unblinded as described below. The Dose Escalation Committee will include sponsor and contract research organization (CRO) representatives.

4.1.1. Number of Subjects

A maximum of 40 subjects will be randomized in the study (up to 5 cohorts of 8 subjects each); within each cohort, 6 subjects will be randomized to IW-3300 and 2 subjects will be randomized to placebo.

4.1.2. Intervention Groups and Duration

The study will evaluate single ascending doses of IW-3300 in a double-blind manner. The 8 subjects within each cohort will be randomized to receive a single dose of IW-3300 (6 subjects) or placebo (2 subjects), administered rectally (as a low-volume [20 mL] enema) following a fast of at least 6 hours (refer to the Schedule of Activities [SoA], Section [12.3](#) for additional details regarding dosing instructions). The planned cohorts are:

[figure not shown]
- Cohort 1: 100 µg IW 3300 or matching placebo single rectal dose
- Cohort 2: 300 µg IW 3300 or matching placebo single rectal dose
- Cohort 3: 900 µg IW 3300 or matching placebo single rectal dose
- Cohort 4: 2500 µg IW 3300 or matching placebo single rectal dose
- Cohort 5 (optional): ≤ 2500 µg IW 3300 or matching placebo single rectal dose (specific dose level to be determined after safety reviews of previous cohorts; doses higher than 2500 µg will not be tested)

In Cohort 1, sentinel dosing will be implemented. The first 2 subjects will be randomized in a 1:1 ratio to IW-3300 or placebo and dosed at least 4 hours before the remaining subjects in the cohort. If no safety signals are noted following an observation period of at least 4 hours postdose, the remaining 6 subjects in Cohort 1 will be dosed. Dosing in Cohorts 2 through 5 will only proceed following a review of the prior dosed cohort(s), including adverse events (AEs), clinical laboratory test results, vital signs, and 12-lead ECGs. The determination of dose escalation will be made at a meeting of the Dose Escalation Committee.

Treatment duration will be 1 day; subjects will be followed in the Phase 1 clinical research unit (CRU) for approximately 24 hours after dosing and contacted by phone for follow-up approximately 2 weeks after dosing. Total subject participation will be 22 to 45 days, including the Screening, Clinic, and Follow-up Periods.

The schematic of the study design is presented below ([Figure 1](#)).

Figure 1: Schematic of Study Design

4.2. Discussion of Study Design, Including Choice of Control Group

A randomized, double-blind, placebo-controlled study design was chosen to investigate the safety, PK, and PD of IW-3300, and to determine the tolerability of a range of doses of IW-3300 administered rectally as a low-volume enema. Subjects will be randomized within each cohort to ensure that the treatment groups are comparable and to minimize the potential for selection bias. The study will be double-blind to ensure that the subjects and CRU staff are unaware of the treatment assignment and to minimize the potential for bias in study assessments or AE reporting. Placebo was chosen as the control so that the rate of spontaneously occurring AEs can be determined and to reduce the potential for bias in the reporting of AEs.

Subjects will complete the BM portion of the BBMD during the last 7 days of the Screening Period to establish a baseline without study drug. Subjects will be confined to the CRU for the duration of the Clinic Period, from Check-in (Day -1) through 1 day of dosing until Discharge (Day 2), which will occur after completion of the assessments (at least 24 hours after administration of study drug) and at the investigator's discretion. CRU staff will contact subjects for the Follow-up Phone Call 12 (+3) days after Discharge for safety follow-up; at the discretion of the investigator, subjects may be requested to return to the CRU for their follow-up contact.

Because this is the first-in-human study with IW-3300, Cohort 1 will feature sentinel dosing whereby the first 2 subjects will be randomized in a 1:1 ratio to receive IW-3300 or placebo, and they will be dosed at least 4 hours before the remaining subjects in the cohort. Subsequently, the cohorts will be enrolled sequentially, following a safety review of prior dosed cohorts. In addition, stopping criteria have been established to ensure that dosing at the same or higher dose levels (a lower dose could be used) will stop should a safety signal be detected.

4.3. Method of Assigning Subjects to Treatment Groups

Randomization numbers encoding the subjects' treatment assignments will be based on a randomization schedule that is computer-generated; the randomization schedule will be generated prior to the study, by an independent statistician from a CRO who is not otherwise associated with the study.

4.4. Blinding

The investigator and all other CRU staff, sponsor study personnel, and the subject will remain blinded to individual subject treatment assignments throughout the study, except as noted below.

The Dose Escalation Committee, which will include sponsor and CRO representatives, will conduct blinded reviews of all the safety/tolerability parameters of the dosing cohort through Discharge (Day 2) in order to make decisions regarding dose escalation.

Specific designated personnel in the Ironwood may be unblinded to the treatment assignment of individual subjects for regulatory reporting purposes. All other sponsor study personnel, except as described, will remain blinded until the study is complete and the database is locked, unless warranted by emerging safety or tolerability issues.

The designated independent study statistician, who will not be involved in study data analysis and interpretation, will have access to the randomization schedule including treatment assignments.

Specifically designated unblinded CRU pharmacy staff will be responsible for preparing dosing for each cohort and providing doses to the study coordinator to administer to subjects. The investigator (except as detailed here) and the remaining CRU staff will be blinded as to treatment. In the event of a Quality Assurance audit, the auditor(s) will be allowed access to unblinded study intervention records at the CRU to verify that randomization/dispensing has been done accurately.

Site unblinding of a subject's treatment assignment is restricted to emergency situations that necessitate identifying the study drug for the welfare of the subject. Subject safety must always be the first consideration in making such a determination. If the investigator decides that unblinding is warranted, the investigator, or person designated by the investigator, should contact the sponsor's medical monitor directly to discuss the need for emergency unblinding. Individual sealed unblinding envelopes, which can be opened to identify the treatment assignment for an individual subject in an emergency, will be provided to and retained by the CRU pharmacist. The reason for breaking the blind will be recorded.

4.5. Sample Size and Power Considerations

No statistical sample size determination process was performed. The sample size chosen for each cohort (8 subjects) is considered sufficient for evaluation of safety, tolerability, PK, and PD.

5. STATISTICAL ANALYSIS SETS

5.1. Screened Set

The Screened Set consists of all subjects who signed the informed consent.

5.2. ITT Set

The ITT Set consists of all subjects in the Screened Set who have been randomized to a treatment regimen. Analysis will be performed according to the allocated treatment regimen regardless of the treatment regimen actually received.

5.3. Safety Analysis Set

The Safety Analysis Set consists of all subjects who received any amount of study drug. Analysis will be performed according to the treatment actually received regardless of the allocated treatment.

5.4. PK Analysis Set

The PK Analysis Set consists of all subjects in the Safety Analysis Set who have at least 1 postdose PK assessment. Analysis will be performed according to the treatment actually received regardless of the allocated treatment.

5.5. PD Analysis Set

The PD Analysis Set consists of all subjects in the Safety Analysis Set who have at least 1 postdose BBMD entry in the Clinic Period. Analysis will be performed according to the treatment actually received regardless of the allocated treatment.

All subjects on placebo arm will be pooled from available cohorts, whenever appropriate, to conduct analyses. All data will be summarized by cohort or treatment group, whenever it is appropriate.

6. STUDY SUBJECTS

6.1. Disposition of Subjects

The number and percentage of subjects who were included in each defined analysis set (ie, Screened, ITT, Safety, PK, and PD) will be summarized by treatment group and overall, except for the Screened Set, which will only be summarized overall.

In rare instances, a subject may withdraw from the study prior to completion of the Clinic Period. The number and percentage of subjects who completed or who prematurely discontinued will be presented for each treatment group and overall for the Safety Analysis Set. Reasons for premature discontinuation as recorded on the termination page of the eCRF will be summarized (number and percentage) by treatment group and overall.

6.2. Demographic and Other Baseline Characteristics

Descriptive summaries of demographic and baseline characteristics will be presented by treatment group and overall, for the Safety Analysis Set.

The following demographic characteristics will be summarized in the tables: age (years and by category), sex, ethnicity, race, weight, height, and BMI.

6.3. Medical and Surgical History

Medical and surgical history will be collected at the Screening Visit and will be coded using MedDRA Version 24.0. A data listing will be provided for the Safety Analysis Set.

The medical history will be summarized by system organ class (SOC) and preferred term (PT) for each treatment group and overall, for the Safety Analysis Set.

6.4. Prior Medications, Therapies, Procedures

Prior medications will be coded using the WHO Drug Dictionary dated 03 March 2020. Prior therapies and procedures will be coded using MedDRA Version 24.0.

Prior medications, therapies, and procedures are defined as that with a start date prior to the date of the first dose of study drug.

The prior medication, therapy, and procedure usage will be summarized by the number and percentage of subjects in each treatment group and overall, within each preferred term for the Safety Analysis Set. Multiple uses of the same medication, therapy, or procedure by a subject in the same category will be counted only once.

All prior medications, therapies, and procedures will be listed for the Safety Analysis Set.

6.5. Concomitant Medications, Therapies, and Procedures

Concomitant medications will be coded using the WHO Drug Dictionary dated 03 March 2020. Concomitant therapies and procedures will be coded using MedDRA Version 24.0.

Concomitant medications, therapies, and procedures are defined as those with a start date prior to the date of the first dose of study drug and continuing on or after the first dose of study drug, or

with a start date between the dates of the first and last doses of study drug, inclusive. Any medication, therapy, or procedure with a start date after the date of the last dose of study drug will not be considered a concomitant medication, therapy, or procedure.

The concomitant medication, therapy, and procedure and usage will be summarized by the number and percentage of subjects in each treatment group and overall, within each preferred term for the Safety Analysis Set. Multiple uses of the same medication, therapy, or procedure by a subject in the same category will be counted only once.

All concomitant medications, therapies, and procedures will be listed for the Safety Analysis Set.

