6.1.1. Dosing Instructions

Subjects will receive a single dose of study drug (IW-3300 or placebo low-volume enema) in the CRU on Day 1. Study drug will be administered rectally after a fast of at least 6 hours. Subjects will be encouraged to empty their bowels in the morning prior to dosing, if possible. Subjects will be instructed to lie on their left side with their left leg extended and their right leg slightly bent. CRU staff will remove the cap from the applicator tip and gently insert the tip into the subject's rectum, then slowly squeeze the bottle to empty the contents into the rectum. After using the enema, subjects will lie on their left side for at least 30 minutes to allow the liquid to distribute throughout their intestines, followed by at least 30 additional minutes in the semisupine position. CRU staff will monitor subjects for leakage of the study drug from the rectum during the initial 30 minutes post administration. Subjects should avoid using the bathroom and hold in the enema for as long as possible (at least 1 hour).

CRU staff will record the date and time of study drug administration in the electronic case report form (eCRF). CRU staff will also record (as yes/no) if there was study drug leakage from the rectum in the 30 minutes following drug administration.

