6.5. Concomitant Therapy

Subjects must abstain from taking prescription medications during the 14 days before Check-in (Day -1) until after completion of the Follow-up Phone Call on Day 14; over-the-counter medications (including laxatives, vitamins, and dietary or herbal supplements) during the 7 days before Check-in (Day -1) until after Discharge on Day 2; and vaccines during the 30 days before Check-in (Day -1) until after completion of the Follow-up Phone Call on Day 14.

Acetaminophen at doses of ≤ 3 grams/day is permitted for use during the study at the investigator's discretion, in consultation with the medical monitor.

Any medication (including over-the-counter or prescription medicines, vitamins, and/or herbal supplements) or vaccine that the subject is receiving at the time of Screening or receives during the study must be recorded along with:

- Reason for use
- Dates of administration, including start and end dates
- Dosage information, including dose and frequency

The medical monitor should be contacted if there are any questions regarding concomitant or prior therapy.

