9.4.2. Primary Endpoints Analyses

The primary endpoint analysis will be based on the Safety Analysis Set.

AE verbatim terms will be coded in the electronic data capture (EDC) system against the most current version of the Medical Dictionary for Regulatory Activities (MedDRA) available at the start of the study.

TEAEs are defined in Section 10.3.1. The TEAEs and TESAEs for 1 calendar day postdose will be summarized by system organ class, preferred term, and treatment (or cohort).

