7.1. Adverse Events

AEs will be coded by SOC and PT using MedDRA Version 24.0. The study investigator will assess the severity of the AE and assign a grade using the Common Terminology Criteria for Adverse Events (CTCAE). An AE is considered a treatment-emergent AE (TEAE), if the AE started after initial study drug administration and within 1 day of the last dose of study drug. In addition, an AE that started before initial study drug but worsened after the first dosing of the study drug is also considered a TEAE.

The number and percentage of subjects reporting TEAEs in each treatment group will be tabulated:

- by SOC and PT
- by SOC, PT, and CTCAE grade
- by SOC, PT, and relationship to study drug.

If a subject has more than 1 TEAE coded to the same PT, the subject will be counted only once for that PT by identifying the TEAE with the highest CTCAE grade and the closest relationship to study drug.

The incidence of the following TEAEs will be summarized by PT:

- Treatment-emergent Serious Adverse Events (TESAEs)

All AE summary tables will be sorted alphabetically by SOC and each PT within the SOC will be sorted by decreasing frequency for the IW-3300 group.

A TEAE summary table with all the non-SAEs by SOC and PT will be generated to support the clinicaltrials.gov reporting requirements.

AE listings will be presented for all subjects with AEs, all screened subjects with SAEs, all SAEs (regardless of treatment-emergent status), and subjects who died (if any), respectively.

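### Medications, therapies and procedures first started on Day 2 or later fall outside both SAP definitions and so enter no planned medication table or listing

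*SAP*

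**What the plan says.** SAP 6.4 sets the first class: "Prior medications, therapies, and procedures are defined as that with a start date prior to the date of the first dose of study drug". SAP 6.5 sets the second, with two routes in: an item that began before the first dose and was still in use on or after it, or an item whose start falls from the first to the last dose date inclusive. The section then closes the window: "Any medication, therapy, or procedure with a start date after the date of the last dose of study drug will not be considered" concomitant. Each section plans a table and a listing for its own class. The SAP defines no third class and plans no listing of all recorded medications.

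Both documents describe a single administration. SAP 4.1.2 states "The 8 subjects within each cohort will be randomized to receive a single dose of IW-3300" or placebo, and Protocol 6.1.1 states "Subjects will receive a single dose of study drug", given on Day 1.

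Collection goes further than reporting. Under Protocol 6.5, any medication, supplement or vaccine a subject "receives during the study must be recorded along with" its reason, dates and dosage. The Schedule of Activities (Protocol Table 1, repeated in SAP 12.3) marks concomitant medications through the follow-up call on Day 14 (+3).

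**The concern.** A window running from first to last dose makes sense when dosing continues for days or weeks. With one dose it shrinks to a single calendar date. The primary objective of this first-in-human trial is safety and tolerability, and a reader of the study report will expect to see what was given to subjects after dosing.

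The medication window is also narrower than the adverse event window. SAP 7.1 counts an event as treatment-emergent "if the AE started after initial study drug administration and within 1 day of the last dose of study drug", and Protocol 9.4.2 says "The TEAEs and TESAEs for 1 calendar day postdose will be summarized". Both windows reach into Day 2. A TEAE that begins on Day 2 is tabulated, but a drug started that day to treat it is not. The same holds for treatment started on Day 2 for a TEAE that began on Day 1.

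The uses most likely to go unreported are the permitted ones, because they would not appear as deviations: acetaminophen allowed by the investigator (Protocol 6.5), prescription drugs in a medical emergency, and over-the-counter products or supplements after Discharge (Protocol 5.2.2). Non-drug therapies and procedures belong here too, to the extent that they are collected.

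**Working it through.** The plan states no figure to reproduce. The check applies the date rules of SAP 6.4 and 6.5 to this design.

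**Inputs**
- One dose, on Day 1 (Protocol 6.1.1; SAP 4.1.2). First-dose date = last-dose date = Day 1.
- The next calendar date is Day 2 (SAP 12.1.3).
- Follow-up call on Day 14 (+3), so Day 17 at the latest (Protocol 4.1.1.3).

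**Rules with the dates put in**
- Prior: start < Day 1.
- Concomitant: start < Day 1 and continuing on or after dosing; or Day 1 ≤ start ≤ Day 1.

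| Start | Stop | Prior? | Concomitant? |
|---|---|---|---|
| before Day 1 | before Day 1 | yes | no |
| before Day 1 | Day 1 or later | yes | yes |
| Day 1 | any | no | yes |
| Day 2 | any | no | no |
| Day 14 or Day 17 | any | no | no |

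**Count of days**
- Call on Day 14: 14 calendar days from Day 1; 14 − 1 = 13 have no class.
- Call on Day 17: 17 calendar days from Day 1; 17 − 1 = 16 have no class.

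These are possible start dates for a subject who completes follow-up. They are not a share of records.

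**Comparison with the TEAE window (clock times assumed).** Suppose an event begins at 02:00 on Day 2 and treatment for it starts at 02:30.
- Dose at 09:00 on Day 1: onset is 15 h to midnight + 2 h = 17 h postdose.
- Later-dosed Cohort 1 subject, dose at 09:00 + 4 h = 13:00: onset is 11 h + 2 h = 13 h postdose.

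In both cases the event is a TEAE whether one day means 24 hours or one calendar day. The treatment has a Day 2 start and is excluded. An event later on Day 2 can depend on the reading: with a 09:00 dose, onset at 10:00 on Day 2 is 25 h postdose, a TEAE on the calendar-day reading only. The exclusion of the medication does not change, because SAP 6.5 works by date.

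**Other SAP text that might catch these items**
- SAP 5.5 ends with a general statement that data are summarized by cohort or treatment group where appropriate. It creates no class or listing and does not undo the express exclusion in 6.5.
- SAP 6.7 lists protocol deviations. That may show prohibited use, but not permitted use.
- SAP 12.1.5 applies the adverse event date rules to incomplete dates only. A partial date could therefore be handled differently from a known Day 2 date.

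**The case against.** The strongest reply is that the exclusion is deliberate. It is written out in full, treatment lasts one day, and restricting the label to items that overlap treatment is a coherent convention. The sentence governs a label and does not discard data. Protocol 9.4 promises no medication summary, so nothing is contradicted. All of that is right, but it leaves the gap in place: a sponsor who keeps the narrow label still has no output for the remaining items.

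The second reply is that the mismatch with the TEAE window covers Day 2 only. From Day 3, newly starting events are outside the TEAE tables as well. Before Discharge on Day 2, permitted use is essentially acetaminophen or an emergency prescription, and an emergency should also surface in adverse event reporting. This stands, and it limits the argument from the TEAE window to one calendar day. The case for the later days rests on the recording rule, the schedule, and the SAP 7.1 commitment that "AE listings will be presented for all subjects with AEs", which is not confined to the TEAE window. Whether that listing shows treatment given is not stated.

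Third, the cited recording rule covers medications, supplements and vaccines. It does not establish that therapies or procedures starting after dosing are collected, so that part is conditional. Finally, with at most 40 healthy volunteers, the number of affected records could be zero. That cannot be excluded.

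**Conclusion.** The concern holds, at minor severity. Followed exactly, SAP 6.4 and 6.5 leave every item with a known start on Day 2 or later out of every planned medication table and listing, although the protocol requires such medications to be recorded. This is a gap in planned output and not a conflict with the protocol.

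The conclusion rests on one dose per subject and on known start dates. The 13 to 16 unclassed days assume a completed follow-up. The documents give no medication-use rates, so no number or percentage of records can be stated. TEAE and TESAE incidence and CTCAE grades are unchanged, and the escalation inputs named in Protocol 6 do not include medications. What is lost is completeness of the supportive safety record.

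**What to change.** Amend SAP 6.5 before database lock in one of two ways.

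1. Remove the exclusion of later starts and define as concomitant any medication, therapy or procedure used on or after the dosing date, through the Follow-up Phone Call or early termination.
2. Keep the present definition and add a post-treatment category for items starting after the dosing date, with its own table and listing.

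The second option suits a sponsor who wants to keep the narrow label. Extending only to Day 2 would match the TEAE window but would still leave later recorded items unreported. A single listing of all recorded medications would close the listing gap but not the table gap.

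The cost is one changed definition, or one added category with a table and a listing. The medication data are already being collected.
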